## Division & Personnel

### Division

What Division/Department does the PI belong to?  
Substance Abuse  
Within the division/department, what Center or group are you affiliated with, if any?  
Biological Studies Unit

### Unaffiliated Personnel

List investigators, if any, who will be participating in this protocol but are not affiliated with New York State Psychiatric Institute or Columbia University. Provide: Full Name, Degrees and Affiliation.  
No co-investigators

## Amendment

Describe the change(s) being made

To add Craigslist to the recruitment options.

Provide the rationale for the change(s)

We are seeking an alternative to print or radio ads.

Comment on the extent to which the proposed change(s) alter or affect risks/benefits to subjects

It doesn't.

Comment on if the proposed change(s) require a modification to the Consent Form (CF)

It doesn't.

## Procedures

**To create the protocol summary form, first indicate if this research will include any of the following procedures**

- ✓ Medication Trial
- ✓ Use of Investigational Drug or Device

## Population

**Indicate which of the following populations will be included in this research**

- ✓ Adults
- ✓ Adults over 50

## Research Support/Funding

Will an existing internal account be used to support the project?

No

Is the project externally funded or is external funding planned?

Yes

Select the number of external sources of funding that will be applicable to this study

## Funding Source #1

Is the PI of the grant/contract the same as the PI of the IRB protocol?

No

Who is the PI of the grant/contract?

[name]

Select one of the following

The grant/contract is currently funded

Source of Funding

Federal  
Institute/Agency

NIDA

Grant Name

K24

Grant Number

DA029647

Select one of the following

Single Site

Business Office

CU

Does the grant/contract involve a subcontract?

No

## Study Location

Indicate if the research is/will be conducted at any of the following

NYSPI

This protocol describes research conducted by the PI at other facilities/locations

No

## Lay Summary of Proposed Research

Lay Summary of Proposed Research

This project will evaluate the effect of one or two sub-anesthetic infusions of ketamine (0.11 mg/kg 2-min bolus followed by 0.6 mg/kg over 50 minutes or 1.3 mg/kg over 90 minutes) in 15 treatment-seeking cannabis-dependent individuals receiving motivational enhancement therapy (MET) and mindfulness-based relapse prevention (MBRP) therapy, using a 6-week single-blind, open label trial.

During the first two weeks of study, the participants will receive MET. In Week 2, Day 2, the participants will be asked to initiate abstinence, and receive a single infusion of ketamine on the day of abstinence initiation. In weeks 3-6, the participants will receive MBRP. If the participants are not doing well, they will receive a second infusion of ketamine in Week 4, Day 2.

In addition to measures of mindfulness and impulsivity, stress sensitivity tests are incorporated into the design in order to elucidate mechanisms of action.

## Background, Significance and Rationale

### Background, Significance and Rationale

This proposal will focus on treating cannabis use disorders with a one or two sub-anesthetic infusions of ketamine (0.11 mg/kg 2-min bolus followed by 0.6 mg/kg over 50 minutes or 1.3 mg/kg over 90 minutes), a high-affinity non-competitive N-methyl-D-aspartate receptor (NMDAR) antagonist. Our preliminary research suggests that ketamine improves dependence-related vulnerabilities common to a variety of substances. We have shown that a single infusion improves motivation to quit, reduces cue-induced craving, improves non-reactivity, and reduces cocaine self-administration among non-treatment cocaine dependent individuals. We have also shown that ketamine infusions can be integrated into outpatient behavioral treatment, such as motivational enhancement therapy (MET) and mindfulness-based relapse prevention (MBRP), to address cocaine use disorder and alcohol use disorder. This includes a protocol with cocaine users that provides up to 2 ketamine infusions. In these protocols, some individuals who had been using cannabis problematically in addition to the substance for which they sought treatment stopped using cannabis.

In this single blind, open label trial, we extend the treatment model we have developed to treat cocaine use disorder to the treatment of cannabis use disorder, with the expectation that we will observe similar feasibility. This protocol includes a manualized sequence of MET and MBRP in conjunction with up to 2 infusions of ketamine. The primary outcome is tolerability of study medications.

## Specific Aims and Hypotheses

### Specific Aims and Hypotheses

The primary purpose of this study is to assess whether giving one or two sub-anesthetic dose of ketamine to cannabis users will be feasible.

## Description of Subject Population

### Sample #1

Specify subject population

Cannabis dependent individuals

Number of completers required to accomplish study aims

15

Projected number of subjects who will be enrolled to obtain required number of completers

20

Age range of subject population

21-60

### Gender, Racial and Ethnic Breakdown

Based on the demographic distribution of cannabis dependent individuals, we expect that our sample will be 45% Caucasian, 25% Hispanic, 25% African American, and 5% other racial groups. Approximately 30% of the sample will be female. This profile is also representative of clinical trials at our institution and elsewhere targeting cannabis dependent treatment-seeking individuals. This study does not exclude participants on the basis of race and gender, and it seeks to include women and minorities

### Description of subject population

Patients will be considered eligible if they are medically healthy, cannabis dependent individuals who meet minimum use criteria, who are between the ages of 21 and 60, and who do not have a history of abuse of or adverse reaction to ketamine or benzodiazepines. Individuals with physiological dependence on certain other substances, with a history of psychotic or dissociative symptoms, with a first-degree family history of psychosis, with obesity (BMI > 32), or with cardiovascular or pulmonary disease will be excluded.

**Pregnant women, women who plan to get pregnant, and lactating women will be excluded.**

## Recruitment Procedures

Describe settings where recruitment will occur

Adult male and non-pregnant female patients will be recruited in the New York City metropolitan area.

How and by whom will subjects be approached and/or recruited?

The advertisements that will be used to recruit participants will be submitted to the IRB prior to the initiation of recruitment procedures. Additionally, prospective participants are recruited by word of mouth and through liaison with other collaborating clinical services, and through ongoing inpatient studies of cannabis self-administration conducted at the Substance Use Research Center (SURC) in our division. All patients are seen by one of our psychiatrists or staff for a screening evaluation and mental status examination as part of routine admission procedures at the BSU. Patients who are cannabis dependent and appear to meet criteria are told about the study and offered further evaluation. Final informed consent is obtained after full psychiatric and medical workup is complete.

How will the study be advertised/publicized?

The study will be advertised by newspaper, radio, television, **Craigslist**, and subway advertisements, as well as on a lab-specific website.

Do you have ads/recruitment material requiring review at this time?

Yes

Does this study involve a clinical trial?

Yes

Please provide the NCT Registration Number

NCT02946489

## Concurrent Research Studies

Will subjects in this study participate in or be recruited from other studies?

No

## Inclusion/Exclusion Criteria

Name the subject group/sub sample

Marijuana dependent individuals

Create or insert table to describe the inclusion criteria and methods to ascertain them

### Inclusion Criterion

1. Meets DSM-IV criteria for cannabis dependence, with at least 5 days of use per week over the past 30 days and displaying at least one positive utox during screening

Method of Ascertainment: MINI, psychiatry interview, self-report, utox

2. Physically healthy

Method of Ascertainment: Laboratory tests (urinalysis, blood chemistry, 12-lead ECG within normal limits, TB test), physical examination, self-reported medical history

3. No adverse reactions to study medications

Method of Ascertainment: Subjects will be asked about previous exposure to ketamine and midazolam

4. 21-60 years of age

Method of Ascertainment: Self-reported age, verification with legal identification

5. Capacity to consent and comply with study procedures

Method of Ascertainment: A short written test about study procedures, MINI, psychiatric interview

6. Seeking treatment

Method of Ascertainment: Psychiatric interview, self-report

Create or insert table to describe the exclusion criteria and methods to ascertain them

### Exclusion Criterion

1. Meets DSM IV criteria for current major depression, bipolar disorder, schizophrenia, any psychotic illness, including substance-induced psychosis, and current substance-induced mood disorder with HAMD > 12.

Method of Ascertainment: Psychiatric Interview, MINI, HAMD

2. Physiological dependence on another substance requiring medical management, such as alcohol, opioids, or benzodiazepines, excluding caffeine, and nicotine

3. Pregnant, interested in becoming pregnant, or lactating

Method of Ascertainment: Blood and urine pregnancy testing, self-report

4. Delirium, Dementia, Amnesia, Cognitive Disorders, or dissociative disorders

Method of Ascertainment: MINI, Psychiatric Interview

5. Current suicide risk or a history of suicide attempt within the past 2 years

Method of Ascertainment: MINI, Psychiatric Interview

6. On psychotropic or other medication whose effect could be disrupted by participation in the study

Method of Ascertainment: Psychiatric Interview, self-reported medical history

7. Recent history of significant violence (past 2 years).

Method of Ascertainment: MINI, Psychiatric Interview

8. Heart disease as indicated by history, abnormal ECG, previous cardiac surgery.

Method of Ascertainment: Laboratory tests (12-lead ECG in normal limits), physical examination, self-reported medical history

9. Unstable physical disorders which might make participation hazardous such as end-stage AIDS, hypertension (>140/90), anemia, pulmonary disease, active hepatitis or other liver disease (transaminase levels < 2-3 X the upper limit of normal will be considered acceptable), or untreated diabetes

Method of Ascertainment: Laboratory tests (urinalysis, blood chemistry, 12-lead ECG in normal limits, TB test), physical examination, self-reported medical history

10. Previous history of ketamine or benzodiazepine abuse, and/or a history of adverse reaction/experience with prior exposure to ketamine or benzodiazepines

Method of Ascertainment: MINI, Psychiatric Interview

11. BMI > 35, or a history of undocumented obstructive sleep apnea

Method of Ascertainment: Physical exam, self-reported medical history

12. First degree relative with a psychotic disorder (bipolar disorder with psychotic features, schizophrenia, schizoaffective disorder, or psychosis NOS)

Method of Ascertainment: MINI, Psychiatric Interview

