## Consent Procedures

Is eligibility screening for this study conducted under a different IRB protocol?

No

Describe procedures used to obtain consent during the screening process

At the first contact, a standardized telephone interview will be conducted, and patients who preliminarily meet entry criteria will be scheduled for a first screening visit, during which the patient will give informed consent to provide a urine sample for toxicology and urinalysis, and to undergo a Mini International Neuropsychiatric Interview (MINI), with a psychiatrist for a medical and psychiatric evaluation, as well as completion of the Hamilton Depression Scale (HAM-D) and Dissociative Experiences Scale (DES), and if still eligible, with a research assistant for serum collection (CBC, thyroid panel, Chem 20 panel including liver function tests, serum cortisol) and other diagnostic tests (EKG). We are requesting a waiver of documentation of consent (45 CFR 46.117 (c) (1)) for the phone screen only, given that a consent form for a phone screen would be the only record linking the subject and the research.

Describe Study Consent Procedures

Eligible participants will undergo an interview with one of the consenting physicians, during which information about the study will be provided. Participants will then be asked to read the consent form on their own, after which they complete a quiz and have an opportunity to ask questions. Participants will be considered eligible if they are medically healthy, cannabis dependent individuals who meet minimum use criteria, who are between the ages of 21 and 60, and who do not have a history of abuse of or adverse reaction to ketamine or benzodiazepines. Individuals with physiological dependence on certain other substances, with a history of psychotic or dissociative symptoms, with a first-degree family history of psychosis, with obesity (BMI > 32), or with cardiovascular or pulmonary disease will be excluded. Please consult the full table of inclusion/exclusion criteria in the Human Subjects section for more details.

Indicate which of the following are employed as a part of screening or main study consent procedures

Consent Form

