## Assessment Instruments

Create a table or give a brief description of the instruments that will be used for assessment

**Interviews:** Mini International Neuropsychiatric Interview (MINI): A semi-structured diagnostic interview designed to assist researchers in making reliable DSM-IV psychiatric diagnoses (45 min); Clinician Administered Dissociative States Scale (CADSS): A 23 item clinician administered instrument used to measure current dissociative symptoms (5 min); Dissociative Experiences Scale (DES): A 28 item questionnaire for assessing the extent of daily dissociative experience, modified to be administered by a clinician (5 min); Brief Psychiatric Rating Scale (BPRS) for positive symptoms: A 4 item subscale for assessing psychosis (1 min); Hood Mysticism Scale (HMS): a 32 item scale for assessing infusion-dependent mystical experience, modified to be administered by study staff (5 min); Five Facet Mindfulness Questionnaire (FFMQ): A 39 item instrument modified to be clinician administered that assesses five mindfulness domains: observing, describing, acting with awareness, non-judging of inner experience, and

non-reactivity (5 min); Timeline Follow-Back (TLFB): a retrospective method of quantifying daily consumption of alcohol and other drugs, assisted by the maintenance of a weekly use diary (5 min); Barratt Impulsiveness Scale (BIS): a 30 item questionnaire used to assess impulsivity, modified to be administered by a clinician (5 min); Adverse Symptom Report (ASR): At each visit, the presence, date of onset, or resolution of adverse effects will be queried and recorded; Clinical Global Impression Scale (CGI): The CGI severity and improvement scales measure the overall clinical status of the subjects and change from baseline; Hamilton Depression Scale (HAM-D): A 21 item instrument used to measure current depressive symptoms; Treatment Service Review (TSR): A 8 item questionnaire that assesses the recent exposure of participants to treatment obtained in the community in excess of what is provided in this protocol; Childhood Traumatic Events Scale (CTES): A 6 item semi-structured interview that assesses childhood trauma prior to age 17.

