Any medical risks from increased blood pressure will be minimized through the careful screening of potential subjects. Subjects will be excluded for baseline hypertension or any history of cardiovascular illness. In addition, an ACLS certified physician will be present during the procedure. Continuous ECG monitoring and pregnancy testing will be provided, as well.

Extensive laboratory experience suggests that sub-anesthetic ketamine generally produces transient effects without any persistent changes, but there are some data suggesting that ketamine, and glutamate modulators in general, may alter the glutaminergic system in such a way as to render vulnerable subjects more likely to

develop psychotic disorders. Previous studies, therefore, have tended to exclude participants with a personal or family history of psychosis in order to reduce the psychiatric risks that ketamine may pose. Accordingly, individuals with a personal or first-degree family history of psychosis will be excluded from this study. Furthermore, the protocol involves close monitoring and an assessment of psychiatric stability prior to discharge; this both ensures that any lingering sedation is allowed to dissipate, and that participants are closely monitored for persistent side effects. Participants will be screened by a psychiatrist and cleared for continued participation following the infusion on Week 2, Day 2, and they will also be followed twice weekly during the following phase of the trial. Subjects will be provided a number to call to reach an on-call psychiatrist (24 hours/day) should unpleasant effects occur after subjects have left the testing facility.

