There is a risk of adverse interactions with the study medications if participants are actively intoxicated on illicit medications. In order to minimize this risk, participants are encouraged to remain abstinent before the infusion, and will be tested daily with urine toxicology. They will also undergo a field sobriety test on the day of the infusion, prior to administration. In addition, they will be evaluated by a clinician ([name]) for DSM-IV signs of any intoxication.

In conclusion, the careful evaluation of participants during the screening process for cardiovascular, psychiatric, medical, and historical vulnerabilities to ketamine infusion; the presence of a psychiatrist with ACLS certification (the PI) during and after the infusion who will monitor for side effects and adverse events; the sub-anesthetic, generally well-tolerated dose at which ketamine will be infused; the close monitoring during infusion; the psychiatric evaluation and clearance to go home; the regular outpatient visits to monitor for persistent effects; and the provision of supportive and pharmacological measures to

address any side effects all ensure that the medical and psychiatric risks involved in participation in this study will be minimal.

2. Blood drawing/Intravenous placement: Another risk in the study is that bruising or a blood clot could form at the site of the intravenous line or venipuncture. Medical staff with extensive experience with IV placement will remain available to ensure that risks are minimized.

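### The summary text excludes past psychotic or dissociative symptoms; the criteria table excludes only psychotic illness and dissociative disorders, and does not say plainly that the illness is lifetime

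*Protocol*

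**What the plan says.** Four places in the protocol bear on a candidate's own psychotic or dissociative history.

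- **Description of subject population** excludes individuals "with a history of psychotic or dissociative symptoms". **Consent Procedures** repeats the same sentence and then adds: "Please consult the full table of inclusion/exclusion criteria in the Human Subjects section for more details". The population description carries no such pointer.
- **Exclusion Criterion table, criterion 1** applies to a candidate who "Meets DSM IV criteria for current major depression, bipolar disorder, schizophrenia, any psychotic illness, including substance-induced psychosis". It ends with substance-induced mood disorder, where the word *current* is used a second time, together with a HAM-D limit. Ascertainment is by psychiatric interview, MINI and HAM-D.
- **Exclusion Criterion table, criterion 4** lists "Delirium, Dementia, Amnesia, Cognitive Disorders, or dissociative disorders", ascertained by MINI and psychiatric interview.
- **Risks/Discomforts/Inconveniences** states that "individuals with a personal or first-degree family history of psychosis will be excluded from this study". It does not mention dissociation here.

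The same risk section counts "the careful evaluation of participants during the screening process for cardiovascular, psychiatric, medical, and historical vulnerabilities to ketamine infusion" among the measures that keep risk minimal.

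**The concern.** An exclusion for past symptoms is wider than one for a diagnosed illness or disorder. If the screener works from the table, someone whom the summary excludes can go forward to a ketamine infusion. If the screener works from the summary, the same person is turned away. Nothing in the protocol says which text prevails.

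For psychosis this touches a stated safeguard. The risk section explains that ketamine may raise the chance of psychotic disorder in susceptible people, and it relies on screening out a history of psychosis for that reason. The eligibility rule also defines the population in whom the primary outcome, tolerability (Background, Significance and Rationale), will be described. Eligibility belongs in the protocol, so a statistical analysis plan would not settle it.

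**Working it through.** No arithmetic applies. The check is to take the wordings in turn and ask what each does with a given candidate.

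| Candidate | Summary sentence (population description, consent) | Risk section | Criteria table |
|---|---|---|---|
| Past psychotic symptoms, never a diagnosis | Excluded | Not clear | Not excluded |
| Past dissociative symptoms, no dissociative disorder | Excluded | Not addressed | Not excluded |
| Past, resolved psychotic illness | Excluded | Excluded | Excluded if criterion 1 is lifetime; not if *current* governs the whole list |
| First-degree relative with psychosis | Excluded | Excluded | Excluded (criterion 12) |

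**Rows 1 and 2: the contradiction.** The table has 12 exclusion criteria. Criteria 1 and 4 are the only ones that deal with a candidate's own psychotic or dissociative condition. None of the other ten closes the gap; criterion 12 concerns relatives only.

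**Row 3: the ambiguity.** In criterion 1, *current* stands before major depression and is repeated before substance-induced mood disorder. The repetition would be unnecessary if the first use covered the whole list. The natural reading is therefore that bipolar disorder, schizophrenia and psychotic illness count at any time in life. On that reading the table agrees with the risk section. The grammar does not force that reading, however, and a screener who took *current* to govern the list would admit someone the risk section excludes.

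**Row 4: no problem.** The family-history rule is broadly consistent throughout, so the inconsistency is confined to personal history.

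**Does the pointer to the table settle it?** It sends the reader to the table for further detail. Detail refines a rule; it should not remove an exclusion that the summary states outright. The summary is also not simply a shortened copy of the table. It gives "with obesity (BMI > 32), or with cardiovascular or pulmonary disease will be excluded", while criterion 11 sets the BMI limit at 35. That shows the two texts are out of step; it does not show which psychiatric wording is intended.

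**Does the screening DES settle it?** Consent Procedures has it completed at screening. Assessment Instruments describes it as "A 28 item questionnaire for assessing the extent of daily dissociative experience", so it measures present daily experience rather than lifetime history. The table sets no exclusion level for it and does not list it as a method for criterion 4.

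**The case against.** The strongest reply is that the table governs. Consent Procedures calls it the full table, and the summary is loose elsewhere: its references to minimum use and to certain other substances cannot be applied without the table. The summary's family history of psychosis becomes, in criterion 12, a list of psychotic disorders that includes psychosis NOS, so what the summary says broadly the table may express at disorder level. If psychosis NOS counts as a psychotic disorder there, it plausibly falls under psychotic illness in criterion 1 too, and the psychotic half of the gap is narrower than it first looks. Candidates also pass a MINI, a psychiatrist's evaluation and a DES, and are cleared and followed after infusion.

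Much of this stands. It makes the table the likelier working document and the gap a narrow one. It does not remove the gap: a history of symptoms is still wider than any diagnosis, the population description has no pointer, and a careful psychiatrist still needs to know which rule to apply.

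Three stronger readings are tempting and are not supported.

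- A reader might infer three incompatible rules, counting the risk section as a third. On the natural lifetime reading of criterion 1, the risk section and the table agree on psychotic illness. The real difference is between symptom level and disorder level.
- A reader might infer that the table knowingly admits people with past psychotic illness. The wording only leaves room for doubt.
- A reader might infer that the safety rationale covers both halves. It is given for a history of psychosis. It does not speak expressly to symptoms below a diagnosis, and no part of the protocol gives a reason for excluding past dissociative symptoms.

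**Conclusion.** The point holds as a wording contradiction in a safety-related exclusion, with an added ambiguity about lifetime psychotic illness. It should be corrected, but it does not undermine the trial.

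Its size cannot be stated. The protocol gives no rate of past psychotic or dissociative symptoms below a diagnosis, so the number of candidates whose eligibility turns on it is unknown and may be none. No sample size or other numerical design figure depends on it.

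The conclusion rests on two readings: that a history of symptoms includes symptoms that never met a diagnosis, and that criterion 4 works at disorder level because it names dissociative disorders. The case for acting is stronger for psychosis, where the protocol relies on the exclusion as a safeguard. For dissociation it is a matter of consistency.

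**What to change.** **Psychosis.** In criterion 1, keep *current* for major depression and substance-induced mood disorder only, and write: *current or past psychotic illness, including substance-induced psychosis, or a history of psychotic symptoms*. Ascertain it by the MINI and psychiatric interview already done. State whether brief symptoms confined to intoxication count. This matters because inclusion criterion 1 requires cannabis use on at least 5 days a week. Lowering the summary to the table's level instead would also end the contradiction, but it would withdraw an exclusion the protocol now states twice, and lifetime illness would still need to be made explicit.

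**Dissociation.** The sponsor should decide between symptom level and disorder level. If symptom level, add a history of dissociative symptoms to criterion 4. If disorder level, change the sentence in the population description and in Consent Procedures. Either way the three places should match. No DES cut-off should be introduced for this purpose, since the scale does not measure lifetime history.

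**Cost.** Wording only, with no new assessment. The wider psychosis rule, and the symptom-level choice for dissociation, may reduce the eligible pool, more so if intoxication-only symptoms count; the protocol does not allow the loss to be sized. The disorder-level choice for dissociation loses no candidates relative to the present table.

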**Infusion Procedures:** One or two ketamine infusions will take place at the BSU within the Division on Substance Abuse. Further, studies with depression have suggested that a single dose has (antidepressant) efficacy. Thus, for the purposes of this study, a single infusion may suffice to affect the outcome measures. If it does not suffice, patients will undergo a second infusion. Patients will be abstinent from intoxicants and will have not eaten since midnight prior to the infusion so as to reduce the risk of nausea, adverse interactions, and aspiration. Participants will be informed throughout the study that they may receive any of a number of substances at the infusion, including buspirone, d-cycloserine, ketamine, midazolam, memantine, saline, or any combination of these. This will serve to further disguise the administration of ketamine, and thereby further minimize the risk that patients will subsequently seek out ketamine. Ketamine hydrochloride (0.11 mg/kg 2-min bolus followed by 0.6 mg/kg over 50 minutes **for the first infusion** and 1.3 mg/kg over 90 minutes **for the second infusion**), will be prepared and packaged for slow-drip infusion by the pharmacy at NYSPI, and will be administered at 12 pm by a physician. The dose of ketamine was selected on the basis of published reports suggesting that it was sub-anesthetic and well-tolerated; it is also comparable to the dose used in the depression studies. Infusions will take place in the presence of an ACLS and BLS certified psychiatrist ([name]) who will remain available for up to two hours after the infusion is terminated and who will provide a brief safety and psychiatric evaluation at the end of the monitoring period. Blood pressure and heart rate will be monitored every five minutes beginning five minutes before the infusion and continuing after the infusion until vital signs normalize; SBP elevation > 60 mm and DBP > 40, or absolute SBP>200 and DBP>115 and HR > (220 – age) X 0.85, will result in infusion discontinuation (please see “Risks” for more information about managing BP or HR). The physician will also be responsible for decisions pertaining to the discontinuation of the infusion in the case of an adverse event. The physician will also be guiding mindfulness-based exercises for the duration of the infusion. A Clinician Administered Dissociative States Scale (CADSS) will be administered following the infusion by the physician or the staff. Ketamine and norketamine (an active metabolite) levels will be obtained at 30 minutes into the infusion and at 60 minutes (20 minutes after the infusion is terminated), the results of which will remain unavailable to all staff for each participant until all assessments are complete. The infusion will be preceded by a urine toxicology to ensure the absence of illicit substance use to minimize the risk of adverse interactions. Female participants will also be tested for pregnancy. Following the infusion, participants will undergo close monitoring, and prior to discharge (occurring at least 3 hrs post-infusion) psychiatric/medical clearance and a field sobriety test.

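### The protocol gives two BMI exclusion limits, > 32 and > 35, so anyone above 32 and up to 35 is both excluded and not excluded

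*Protocol*

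**What the plan says.** A BMI limit appears in three places in the protocol.

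- **Exclusion Criterion, item 11:** "BMI > 35, or a history of undocumented obstructive sleep apnea", ascertained by physical examination and self-reported medical history.
- **Description of subject population:** a narrative summary under which people "with obesity (BMI > 32), or with cardiovascular or pulmonary disease will be excluded".
- **Consent Procedures:** the same summary sentence with the same limit of 32, followed by a pointer: "Please consult the full table of inclusion/exclusion criteria in the Human Subjects section for more details".

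No reason is given for either limit. The Amendment section describes one change, "To add Craigslist to the recruitment options", and does not mention BMI. The Background section states that "The primary outcome is tolerability of study medications".

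**The concern.** An eligibility limit should give one answer for each candidate. Here, enrolling a person with a BMI of 33 conforms to criterion 11 and departs from the two narrative statements. Refusing that person follows the narrative statements, although criterion 11 would not exclude them. Site staff, a monitor and the IRB could each classify the same case differently, and each could cite the protocol in support.

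Two things are at stake. The first is who may be given the infusion. A safety purpose is plausible: criterion 11 pairs BMI with sleep apnea, the summary lists it beside cardiovascular and pulmonary disease, and the Risks section names sedation, tachycardia and raised blood pressure among ketamine's effects. The protocol does not, however, state that purpose. The second is the population that the tolerability result describes. With 15 completers planned, one person of disputed eligibility is 1/15 = 6.7% of them.

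**Working it through.** No sample size, power or error rate is involved. The check is a comparison of the stated rules.

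**Inputs**

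- Rule A (Description of subject population; Consent Procedures): exclude if BMI > 32.
- Rule B (Exclusion Criterion, item 11): exclude if BMI > 35.

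**Comparison**

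| BMI | Rule A | Rule B | Agree? |
|---|---|---|---|
| 32 or below | not excluded | not excluded | yes |
| above 32, up to and including 35 | excluded | not excluded | **no** |
| above 35 | excluded | excluded | yes |

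The people excluded by A but not by B are those with 32 < BMI ≤ 35, a band of 35 − 32 = 3 units. A BMI of exactly 35 falls inside it and a BMI of exactly 32 does not.

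**Does any text settle the conflict?**

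- The pointer in Consent Procedures offers more detail and does not give precedence. Detail can sharpen a vague phrase, but it cannot turn an explicit exclusion above 32 into admission at 34.
- The pointer names a Human Subjects section, whereas the criteria stand under Inclusion/Exclusion Criteria.
- Description of subject population has no pointer.
- The Amendment section covers only the latest change. It shows that this amendment did not alter the BMI limit. It cannot show whether an earlier one did, so it does not reveal which value came first.
- Counting occurrences does not help. The lower value appears twice, but in the same repeated sentence; the higher value appears once, in the numbered list.

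**Which rule is safe to apply meanwhile?** The set admitted by A lies inside the set admitted by B. Anyone with a BMI of 32 or below therefore satisfies the BMI limit in all three sections, whereas applying B can breach two of them.

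**The case against.** The strongest reply is that the numbered list is clearly the operative text. It gives a method of ascertainment for nearly every item. The narrative is visibly abbreviated: it leaves minimum use and the other substances unspecified, and it omits suicide risk, violence and sleep apnea, so nobody could screen from it alone. Consent Procedures then sends the reader to the full table. On this reading one value is simply an editing leftover.

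Much of this stands. Staff would probably screen from the table, and an editing leftover is a likely explanation. It does not remove the conflict, because the summary states a definite number with a definite consequence and the document does not subordinate it.

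A second reply is that little depends on the limit. This also carries weight. Criteria 8 and 9 exclude heart disease, hypertension above 140/90 and pulmonary disease. Vital signs are taken every five minutes with stopping limits, ECG monitoring is continuous, and an ACLS-certified physician is present. No estimate or sample size rests on BMI.

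A third reply is that using > 32 in the interim is only a reviewer's preference. It is not a judgement that 32 is the better value. It is the only one of the two limits that conflicts with none of the three statements.

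**Conclusion.** The contradiction is real and can be seen on direct reading. Candidates with a BMI above 32 and up to 35 have opposite eligibility depending on the section consulted, and the protocol does not say which governs. The affected band is 3 BMI units wide. How many candidates fall in it cannot be derived from the document.

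The consequence is moderate. It concerns who may be infused and how the tolerability population is defined, and other safeguards limit individual risk. With a single arm, no treatment comparison is biased. The finding assumes only that all three sections are current text. It does not say which value is right and does not claim that a BMI between 32 and 35 has been shown to be harmful. The protocol should be corrected because an entry limit for an intravenous ketamine infusion should be unambiguous.

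**What to change.** The investigator confirms the intended BMI limit, and the protocol states it identically in Description of subject population, Exclusion Criterion item 11 and Consent Procedures. Until that is done, screen with > 32 as the exclusion. A sentence in the summary saying that the numbered criteria govern would guard against similar drift.

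The cost is a wording amendment. Keeping 32 changes only criterion 11; keeping 35 changes the two narrative statements. No new assessment is needed, since criterion 11 is already ascertained by physical examination. If 32 is kept, the eligible pool is narrower than criterion 11 now allows, by an amount the protocol does not let one estimate.
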